- Patients: If patients submit an online consultation predicted by AI Triage as emergency at any time or urgent when their GP practice is closed, they immediately receive an automated 'signposting' message advising them to contact emergency services or the NHS 111 'out of hours' service, respectively (Appendix 1, Screenshot 3). They will also be presented with supporting advice from NHS.uk if relevant articles exist on the website. If their online consultation is predicted as 'routine', the patient may be presented with self-help advice from NHS.uk if relevant articles exist on the website (Appendix 1, Screenshot 4). Patients can accept this advice and cancel their online consultation, and the GP practice will not receive the form in their PATCHS inbox but can view it in a

Version 1.1 01/03/2024 IRAS ID: 331286

separate 'cancelled' folder if they wish. Alternatively, patients can ignore the advice and continue to submit their online consultation to their GP practice at their own risk.

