 Proportion of delayed emergency online consultations at the patient-level (disaggregated primary outcome measure; denominator=number of emergency online consultations)

- Proportion of delayed urgent online consultations at the patient-level (disaggregated primary outcome measure; denominator=number of urgent online consultations)
- Proportion of online consultations cancelled by patients at the patient-level (denominator=number of online consultations)
- Proportion of online consultations assigned to clinicians (denominator=total number of online consultations)

Patient-level – continuous

- Absolute time to completion for urgent and emergency online consultations (combined and separate)
- Absolute time to completion for routine online consultations
- Absolute time to first staff user action in online consultation system for urgent and emergency online consultations (combined and separate)
- Absolute time to first staff user action in online consultation system for routine online consultations

GP practice-level – counts (workload measures)

- Proportion of total appointments provided by GP practices (denominator=GP practice population size
 (1))
- Proportion of online consultations submitted by patients (denominator= GP practice population size)
- Proportion of patients with emergency department attendances (denominator=GP practice population size (37))
- Proportion of online consultations with emergency department attendances (denominator=total number of online consultations (37))
- Proportion of patients with emergency hospital admissions (denominator=GP practice population size (37))
- Proportion of online consultations with emergency hospital admissions (denominator=total number of online consultations (37))

GP practice-level – continuous (cost measures)

- Cost of clinicians processing online consultations within the GP practice per 1000 patients
- Cost of emergency department attendances and emergency hospital admissions per 1000 patients

Quantitative process evaluation

For readability, these are described in more detail in the statistical analysis section.

- Fidelity, dose, and reach of Al Triage and online consultations
- Al Triage accuracy, true positive rate, true negative rate, positive predictive value, and negative
 predictive value for predicting urgent and emergency online consultations (combined and separate)
 in intervention GP practices
- Potential triage behaviour change in control GP practices

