We will calculate the overall accuracy (proportion of 'correct' predictions), true positive rate, true negative rate, positive predictive value, and negative predictive value of AI Triage in intervention practices. Our primary measure of accuracy will be for urgent and emergency online consultations combined; secondary measures will assess urgent and emergency online consultations separately. There is no gold standard test to decide the 'correct' triage decision for online consultations written by patients in their own words. We will therefore use the triage decisions made by GP practice staff when processing online consultations and consider their triage decision as 'correct'. Where AI Triage predicts an online consultation as 'urgent' or 'emergency' we will consider it a:

- **True positive** if the triage decision is not changed by staff, or if staff change the triage decision and the highest triage decision applied by staff is 'urgent' or 'emergency'.
- False positive if staff change the triage decision and the highest triage decision applied by staff is
 'routine'.

Where AI Triage predicts an online consultation as 'routine', we will consider it a:

- **True negative** if the triage decision is not changed by staff, or if staff change the triage decision and the highest triage decision applied by staff is 'routine'.
- False negative if staff change the triage decision and the highest triage decision applied by staff is 'urgent' or 'emergency'.

We will quantify cases where emergency online consultations have been predicted as 'routine' as these represent the highest risk misclassifications. The Spectra Analytics Clinical Safety team will investigate these and other patient safety incidents reported by GP practices as per their internal processes to comply with MHRA and NHS DCB0129 standards (16). We will review their findings to understand if there are patient groups or online consultation topics that are at higher risk of misclassification by Al Triage.

Potential triage behaviour change in control GP practices

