We will obtain AI Triage predictions (urgent and emergency – both separate and combined) for control practices for each online consultation submitted during the intervention period and compare them to the actual triage decisions made by GP practice staff using the same definitions of true/false positives/negatives above. These predictions will differ from those in intervention GP practices because they will not have been presented to GP practice staff whilst they processed the online consultations. It identifies a group of patients for whom potentially different triage decisions would have been made if AI Triage had been enabled in those practices. We will then estimate the potential impact of these different triage decisions.

Observed triage behaviour change in intervention and control GP practices

To evaluate observed changes in triage behaviour, we will compare monthly and weekly time series counts of urgent and emergency triage decisions (both separate and combined) made by intervention and control GP practices. In intervention practices we will consider a triage decision as urgent or emergency if the highest triage applied by staff is 'urgent' or 'emergency' or an AI Triage prediction of urgent or emergency is left unchanged (same definition as 'true positives' above). In control practices, we will consider a triage decision as urgent or emergency if the highest triage applied by staff is 'urgent' or 'emergency'. We will also measure counts of patients cancelling their online consultations, and map whether patients cancel their request or receive input from a clinician following a signpost message and/or emergency prediction.

[figure not shown]
Sensitivity analyses

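### The only true/false positive rule merges urgent and emergency, so it cannot give the separate accuracy measures that the protocol promises

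*Protocol*

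**What the plan says.** Section 9 of the protocol lists overall accuracy, true and false classification rates and predictive values for "predicting urgent and emergency online consultations (combined and separate"). Section 11.1, under AI Triage accuracy in intervention practices, makes the combined measure primary and adds that "secondary measures will assess urgent and emergency online consultations separately". It treats the staff decision as the reference standard.

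One set of definitions follows:

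- A form that the AI labels at either of the two higher levels scores as a true positive when staff leave that label alone, or "if staff change the triage decision and the highest triage decision applied by staff is 'urgent' or 'emergency". The two levels are pooled on the AI side and on the staff side.
- Such a form scores as a false positive only when staff alter it and end at routine.
- A form that the AI labels routine scores as a true or a false negative, depending on where staff end up. No other AI label can lead to a negative.

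No definition specific to one class appears. For control practices, Section 11.1 takes AI predictions for the two classes, separately and combined, and scores them "using the same definitions of true/false positives/negatives above".

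The section also commits to counting emergencies that were predicted routine, as the riskiest errors. The error audit, under Health inequalities in the process evaluation, compares false positives and false negatives with true ones.

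**The concern.** AI Triage has three output classes, but the rule is a two-class rule: flagged (urgent or emergency) against routine. That suits the combined measure. It does not suit a measure of how well the AI identifies emergencies, or urgent forms, on their own. Where staff actively move a form between urgent and emergency, they have overruled the AI, yet the AI is scored correct.

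The distinction matters within the protocol. Section 7.2 says patients are signposted when a form is "predicted by AI Triage as emergency at any time or urgent when their GP practice is closed", so the two labels trigger different messages at different times. An AI-urgent form sent during opening hours produces no such message under that description. The labels also differ in inbox position (Section 7.2) and in the delay limit, 24 against 48 hours (Section 9). The validation figures in Section 5 (84% in the test set, 94% in early adopter practices) are for urgent and emergency together. The separate measure would therefore be the only emergency-specific accuracy evidence in this document.

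**Working it through.** The protocol gives no cross-tabulation of AI label by staff label, so there is no figure of its own to reproduce. The check has two parts: how the rule scores each cell, and what follows if it is used for emergencies.

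**1. Scoring the nine cells.** E, U and R stand for emergency, urgent and routine. The staff label is the highest staff decision, or the AI label where staff left it unchanged.

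| AI | Staff | Protocol rule | Emergency vs rest | Urgent vs rest |
|---|---|---|---|---|
| E | E | TP | TP | TN |
| E | U | TP | FP | FN |
| E | R | FP | FP | TN |
| U | E | TP | FN | FP |
| U | U | TP | TN | TP |
| U | R | FP | TN | FP |
| R | E | FN | FN | TN |
| R | U | FN | TN | FN |
| R | R | TN | TN | TN |

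The protocol rule matches an emergency-specific scoring in 4 of 9 cells (EE, ER, RE, RR) and an urgent-specific scoring in 4 of 9 (UU, UR, RU, RR). Applied to all forms, it gives a single true positive rate, (EE + EU + UE + UU) / (EE + EU + UE + UU + RE + RU). That rate is the same whether it is headed combined, urgent or emergency.

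**2. Carrying the rule into an emergency true positive rate.** Restrict to staff-labelled emergencies. Let a, b and c be the numbers the AI called emergency, urgent and routine.

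- Protocol rule: (a + b) / (a + b + c)
- Emergency vs rest: a / (a + b + c)
- Difference: b / (a + b + c), never negative

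All counts below are assumed, because the documents give none.

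- 60/25/15: the rule gives (60 + 25)/100 = 85%; emergency vs rest gives 60/100 = 60%.
- Same counts, taking only AI-emergency as positive but keeping only AI-routine as negative, so that AI-urgent forms drop out: 60/75 = 80%.
- Range with c fixed at 10 of 100:

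| a | b | c | Protocol rule | Emergency vs rest | Difference (points) |
|---|---|---|---|---|---|
| 85 | 5 | 10 | 90% | 85% | 5 |
| 70 | 20 | 10 | 90% | 70% | 20 |
| 50 | 40 | 10 | 90% | 50% | 40 |
| 30 | 60 | 10 | 90% | 30% | 60 |

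The figure under the rule stays at 90% however many emergencies are called only urgent.

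**3. Positive predictive value.** Take 100 AI-emergency labels, with x, y and w labelled emergency, urgent and routine by staff. The rule gives (x + y)/100; emergency vs rest gives x/100.

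- 70/15/15: 85% against 70%
- 50/30/20: 80% against 50%
- 30/50/20: 80% against 30%

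**4. Downstream.** Cells UE and EU are true positives under the rule, so in the intervention-practice error audit they fall in the comparison group and not among the errors. The count of emergencies predicted routine is cell RE only. The control-practice audit (Section 11.1) selects forms where AI and staff differ, which could take in UE and EU. However, it equates these with potential false positives and negatives, which under the rule they are not.

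**The case against.** The strongest reply is that this is a gap in specification and not a wrong result. The rule taken literally yields one pooled table with no emergency denominator. To reach 85%, one must make the staff side emergency-specific while leaving the AI side pooled; the predictive value example does the reverse. The protocol describes neither mixture. An analyst told to report emergencies separately might simply substitute emergency vs rest. The protocol uses urgent-or-emergency as shorthand elsewhere: the triage time series are promised separately and combined but defined only in pooled form, and Section 9 splits its pooled primary outcome by class with class-specific denominators. In control practices the same definitions cannot apply word for word, since staff never saw an AI label to change. A statistical analysis plan, not shown here, could supply the class tables. The count of emergencies predicted routine is a stated priority, and AI-urgent forms are still flagged and moved up the inbox.

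Much of this stands. A reader might infer that the trial's reported emergency detection will be overstated. The documents do not support that as fact: it depends on how the rule is carried over and on a share that they do not give. The count of emergencies predicted routine is also not an error in itself.

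What does not fall away is that the protocol does more than leave a detail open. It states a rule directly after announcing the separate measures, and for control practices it tells the analyst to use the same definitions for separate and combined predictions. A later plan with class-specific tables would have to depart from that wording.

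**Conclusion.** The point holds as a defect in a stated rule for secondary process-evaluation measures. The pooled definitions cannot produce valid separate urgent and emergency accuracy, because disagreements between those two classes are always scored as true positives and only AI-routine forms can be negatives.

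If the rule is carried into the emergency measure, the true positive rate is overstated by the share of staff-labelled emergencies that the AI called urgent. Positive predictive value is inflated by the share of AI-emergency labels that staff lowered to urgent. Both effects are zero only if no such cross-labelling occurs. The direction is certain under that reading; the size is unknown, and the 5 to 60 point range above simply follows the assumed shares. These disagreements would also drop out of the intervention-practice error audit.

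The combined accuracy measure is correctly served by the pooled rule, and the trial's primary outcome does not use these definitions. Neither is affected.

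**What to change.** In Section 11.1, state that the pooled definitions apply to the combined measure only. For the separate measures, in both the intervention-practice accuracy analysis and the control-practice analysis:

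- Report the full 3x3 table of AI label by staff label.
- Define each class one-versus-rest. For emergency: true positive if both say emergency; false negative if staff say emergency and the AI says urgent or routine; false positive if the AI says emergency and staff say urgent or routine; true negative otherwise. Define urgent in the same way.
- Word the control-practice definitions as a comparison of the unseen AI label with the staff label, since there is no displayed label for staff to change.
- Run the error audit on the class-specific errors as well as the pooled ones.
- Report emergencies predicted urgent alongside emergencies predicted routine.

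The cost is wording and one extra table. Section 10 already lists AI predictions and staff triage decisions among the data to be shared, so nothing new is collected. The downside is that the reported emergency figures may be less favourable, and the class-specific results will rest on smaller counts than the combined measure.

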consultation e.g. health problem or administrative. When the form is submitted by the patient it enters an inbox, where GP practice staff can prioritise and respond to online consultations. Patients complete forms in PATCHS by describing their queries in unstructured free text in response to open-ended questions in the system that mimic a typical primary care consultation, as opposed to multiple choice questionnaires. Most (65%) online consultation systems allow patients to describe their queries using unstructured free text [7].

In addition to their query, patients enter their details including sex, ethnicity, home address, email address, and telephone number. Receptionists typically review incoming PATCHS online consultations first, and will deal with any queries they can, and assign those they cannot to other staff within PATCHS, including clinicians, if it requires their input. Patients are then contacted to resolve their query – either by written message or video consultation within PATCHS, telephone or by arranging an in-person appointment. GP practices can assign PATCHS online consultations to future dates to be dealt with by clinicians if deemed necessary to match staffing capacity.

When GP practice staff process patients' online consultations in PATCHS, they record various triage decisions (Appendix 1, Screenshot 1), which have been developed based on qualitative research and workshops conducted with 22 GP practice staff and 37 patients. These triage decisions include whether they believe the online consultation is either:

[figure not shown]
- **Emergency**: patient could be harmed if not resolved within 24 hours and may require immediate care from emergency services.
- **Urgent**: the patient could be harmed if not resolved within the next 48 hours.
- Routine: neither urgent nor emergency.

Analysis of 122,504 PATCHS online consultations submitted to 80 GP practices show that 7922 (6.5%) are urgent or emergency, 25% of which on average are not resolved in the above timelines. We define these as delays in urgent and emergency care: online consultations deemed urgent or emergency by GP practice staff where the difference between the time it was submitted by a patient or their carer in PATCHS and the time it was completed by a staff member is longer than 48 or 24 hours, respectively.

PATCHS AI Triage: development and validation

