Al Triage is available to all GP practices using PATCHS as an optional feature. GP practices must request to have it enabled and undertake specific training on how to use it. Approximately 200 GP practices using PATCHS (20%) currently have Al Triage enabled – the remaining practices use PATCHS without Al Triage. Spectra Analytics are satisfied with the accuracy and clinical safety of PATCHS Al Triage, and plan to offer it to the remainder of practices currently using PATCHS without Al Triage imminently. This presents a unique opportunity to evaluate the impact of Al Triage on delays in urgent and emergency primary care, staff workload, and health inequalities, in a controlled way. This project will also help generate muchneeded high-quality research evidence on Al use in the NHS and aligns with NHS initiatives such as the NHS Al Lab (19). To do this, we (The University of Manchester; UoM) have partnered with Spectra Analytics to conduct a robust study using an interrupted time series analysis and process evaluation.

6) STUDY OBJECTIVES

6.1 Primary Research Question:

1. What is the impact of AI Triage on delays in completing online consultations defined as urgent and emergency by GP practice staff at the patient-level?

6.2 Secondary Research Questions:

Interrupted Time Series Analysis

- 2. What is the impact of AI Triage on the total number of appointments provided by GP practices?
- 3. What is the impact of AI Triage on the number of online consultations submitted by patients?
- 4. What is the impact of AI Triage on the number of online consultations assigned to clinicians?
- 5. What is the impact of Al Triage on emergency department attendances and emergency hospital admissions?
- 6. What are the cost consequences of AI Triage for GP practices and hospitals?

Quantitative Process Evaluation

- 7. What is the fidelity, dose, and reach of AI Triage and online consultations?
- 8. What is the accuracy of AI Triage in intervention practices?
- 9. What is the potential and observed change in triage behaviour?

Both Analyses

10. What is the influence of AI Triage on health inequalities?

7) STUDY DESIGN & PROTOCOL

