In potential behaviour change analyses, we will find patients for whom the AI Triage prediction differs from the actual decision made by GP staff (potential false positives and negatives) and test for differences in characteristics of the patient, online consultation, GP practice staff, and GP practice using the error auditing approach described above (47).

Allocation non-adherence

In a traditional Zelen design, data are analysed on an intention-to-allocate basis rather than whether or not the intervention was actually received (24). This approach is practical when the intervention is not widely available and when participants can provide immediate consent, which is not the case in this study. Firstly, AI Triage has been available to all GP practices using PATCHS since October 2021, therefore control GP practices can start using AI Triage at any time during the study. Because it is considered a selling point, GP practices may also receive communications encouraging them to use AI Triage outside the study e.g. from their NHS commissioning organisation. Secondly, GP practices may take several weeks to reply following an invitation to use AI Triage. Thirdly, GP practices not yet using AI Triage may have explicitly chosen not to use it, meaning they may be more likely to decline an invitation to use it or drop out of the study later. These factors combine to exacerbate our anticipated recruitment challenges described above. Therefore, we will take the following approach:

- Control GP practices that cross over to the intervention group: If we have sufficient follow-up data
 we will treat them as intervention GP practices in the main analysis, otherwise we will use their data
 as controls up to the point they cross over. If numbers allow, we will analyse them separately in an
 uncontrolled interrupted time series analysis. We will conduct sensitivity analyses where we treat
 them control GP practices for the entire study and where we exclude them entirely from the analysis.
- GP practices that decline to use the intervention or do not respond to recruitment communications after being allocated to the intervention group: We will treat them as control GP practices in the main analysis. We will conduct sensitivity analyses where we treat them as intervention GP practices and where we exclude them entirely from the analysis.
- Intervention GP practices that cross over to the control group (i.e. that stop using Al Triage) or stop

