 using PATCHS altogether: We will include them in the main analysis in the intervention group. We
 will undertake sensitivity analyses where we use their data as intervention GP practices up to the
 point they cross over and where we exclude them entirely from the analysis.

11.2 Sample Size:

Our sample size calculation is based on our primary outcome measure. Patients and clinicians we consulted during our PPI work felt an absolute reduction of 5% in the proportion of urgent and emergency online consultation delays would be meaningful. Assuming a baseline delay of 25% from our prior research and a simple before-after design, we estimate a minimum of 2928 urgent and emergency (combined) online consultations across both intervention and control GP practices during the intervention period are required to detect a minimum absolute reduction of 5% to 20% with 90% power and 5% alpha. Further assuming 50 urgent and emergency online consultations (combined) on average for a GP practice per month and a 12-month intervention period, this translates to a minimum of three intervention and three control practices. However, this does not account for between-practice variability. Consequently, we will aim to recruit 20 intervention and 20 control practices. Between-practice variability can be difficult to

predict, so we have estimated the power of this sample size for different assumptions of between-practice variance using ipdpower for Stata (48), which calculates power for mixed-effects models using simulations (Table 1). To minimise between-practice variance in our sample, we will recruit intervention and control GP practices in blocks (described in section 8.4). If we find that between-practice variance is high, we will target recruitment of practices with similar baseline characteristics for the outcome measure in subsequent stages.

Table 1: Study power simulations

Between-practice variance	Power (%)	95% confidence interval (%)
0	100	96.4-100.0
0.1	72	62.1-80.5
0.2	53	42.8-63.1
0.825	21	13.5-30.3

12) DATA AND INTERVENTION ACCESS POST-STUDY

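### Observed triage behaviour is compared as unscaled counts, which can move, or hide a change, with form volume or the number of contributing practices

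*Protocol*

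**What the plan says.** Section 11.1 of the protocol, under the process-evaluation heading on observed triage behaviour change, states: "we will compare monthly and weekly time series counts of urgent and emergency triage decisions". In intervention practices a decision counts if the highest staff triage is urgent or emergency, or if such an AI prediction is left unchanged. In control practices only the staff decision counts. No denominator, offset or scaling is given. The sensitivity analyses that follow vary who decided, which decision is used, cancelled forms and repeat forms; none adds a denominator.

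Other parts of the protocol bear on this:

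- Section 6.2 makes form volume a possible effect of the intervention: "What is the impact of AI Triage on the number of online consultations submitted by patients".
- Section 11.1, under allocation non-adherence, expects controls to take up AI Triage, offered practices to decline, and some practices to stop using PATCHS.
- Section 11.1, for the interrupted time series, gives the other practice-level counts a negative binomial model with offsets for their denominators.
- Section 9 says that the process measures are described in more detail in the statistical section, so section 11.1 is where this one is defined.

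**The concern.** Question 9 asks whether triage behaviour changes, that is, whether a given set of forms is flagged differently. A total of flagged forms answers that only if the number of forms and the number of practices submitting them hold still, and the protocol gives reasons to expect that neither will. Followed as written, the comparison can show a shift when every practice flags the same share of its forms, or show nothing when the share has changed and volume has offset it.

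The flagged forms are also the denominator of the primary outcome, and that denominator is defined differently in the two groups. Knowing whether the flagged share moved therefore helps in interpreting the delay proportion, although it does not alter the primary estimate.

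**Working it through.** **Inputs from the protocol**

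- Practices per group, section 11.2: "we will aim to recruit 20 intervention and 20 control practices".
- Flagged forms, section 11.2: "Further assuming 50 urgent and emergency online consultations (combined) on average for a GP practice per month".
- Flag rate, section 5: "Analysis of 122,504 PATCHS online consultations submitted to 80 GP practices show that 7922 (6.5%) are urgent or emergency".

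**Inputs assumed.** The protocol gives no expected change in volume and no drop-out rate. The 10% changes and the 3 departing practices below are illustrations.

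**Plan's own figures.** 7,922 / 122,504 = 6.47%, which rounds to the stated 6.5%. The 50 per month also fits the plan's arithmetic: 2,928 / 2 = 1,464 per group, and 1,464 / (50 × 12) = 2.44, which rounds up to the stated three practices. No stated figure is in dispute.

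**Formula.** Monthly count = practices × forms per practice × share flagged. At 6.5%, 50 flagged forms imply 50 / 0.065 = 769 forms per practice-month.

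| Situation (one group) | Monthly count | Share flagged |
|---|---|---|
| Planned: 20 × 50 | 1,000 | 6.5% |
| All form volume down 10%: 1,000 × 0.9 | 900 | 6.5% |
| All form volume up 10%: 1,000 × 1.1 | 1,100 | 6.5% |
| 3 of 20 practices leave PATCHS: 17 × 50 | 850 | 6.5% |
| Volume down 10%, share up 10% in relative terms: 1,000 × 0.9 × 1.1 | 990 | 7.15% |

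In the second to fourth rows behaviour is unchanged and the count moves by 10% or 15%. In the last row behaviour changes and the count barely moves.

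**Per-practice scaling alone.** This repairs the fourth row (850 / 17 = 50) but not the volume rows.

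**The proportion under a different change.** Suppose only routine submissions fall, by 10%. Routine forms go from 769 − 50 = 719 to 719 × 0.9 = 647, so total forms are 697. The share becomes 50 / 697 = 7.2%, while the count stays at 50 per practice. Here the proportion moves without any change in how forms are triaged. Neither measure is sufficient alone.

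**The case against.** The strongest reply is that the protocol uses the word counts loosely. Section 9 has a heading for practice-level counts under which every item is a proportion with a named denominator. Submission counts are collected in both groups as dose, and scaling a descriptive measure could be left to a statistical analysis plan that is not shown. In part this stands: the data for a proportion exist, and no test or decision rule is attached to the count. But where the protocol intends a denominator it names one, and here it does not.

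Matching is a second reply. Section 8.4 will try to match on population size, form volume and baseline urgent and emergency prevalence. That limits baseline differences; it cannot hold volume or participation constant afterwards.

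Three stronger readings are tempting, and the documents do not support them:

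- *Reclassification will make the groups grossly unequal.* For decliners the protocol says "We will treat them as control GP practices in the main analysis", and for crossover controls with enough follow-up "we will treat them as intervention GP practices in the main analysis, otherwise we will use their data" as controls until they cross over. If 5 of 20 declined, a reader might infer 15 × 50 = 750 against 25 × 50 = 1,250. But these rules are written for the main analysis, and applying them here is an inference. No decline rate is given, recruitment aims at 20 per group, and a practice becomes an intervention practice only on agreeing. A constant imbalance also shifts the level of a series and not its change over time.
- *Forms cancelled after AI advice vanish from the count.* Section 7.2 says "the GP practice will not receive the form in their PATCHS inbox", but an AI flag left unchanged counts as a decision, and the process-evaluation sensitivity section assumes that predictions for signposted patients who cancel are correct. Such forms may still be counted.
- *Staggered joining distorts the series.* Eligible practices have used PATCHS for at least 12 months, and at least 12 months of data either side of the index date are planned. A series aligned to that date would keep the same practices throughout.

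**Conclusion.** The point holds as a limited one. The stated measure has no denominator, and it changes in direct proportion to form volume and to the number of contributing practices, both of which the protocol allows to change. On the planning figure of 50 flagged forms per practice-month, an assumed 10% fall in volume moves the count by 10%, and an assumed loss of 3 of 20 practices moves it by 15%, with triage unchanged. The loss of practices does not depend on the reclassification rules, because a practice that has left PATCHS makes no decisions in either group.

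The documents do not show that the counts will be misread, or that question 9 is the main evidence on mechanism: accuracy, fidelity, dose and reach, potential behaviour change and a separate qualitative study also contribute. The primary result is untouched.

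**What to change.** In section 11.1, define observed triage behaviour change as the proportion of submitted online consultations that receive an urgent or emergency decision, per practice-month, compared before and after the index date. Take all submitted forms as the denominator, including those later cancelled, defined the same way in both groups and both periods. Report the counts beside it, per practice or per 1000 patients, together with total and routine form volume.

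The cost is a sentence or two of text. Submission times, triage decisions, AI predictions, cancellations and practice codes are already in the section 10 extract. The downside is that the proportion also moves if routine volume alone changes, so it should be added and interpreted with the counts, and should not displace them.
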